# Low-Dose Radiation Therapy for Heterotopic Ossification Prophylaxis in Distal Humerus Fractures

## Purpose:

To determine the effectiveness of 500 cGy dose of radiation therapy vs. an untreated group in the prophylactic treatment of heterotopic ossification in distal humerus fractures

## Hypothesis:

Use of low-dose radiation therapy at a single 500 cGy dose postoperatively will decrease the incidence and severity of heterotopic ossification in distal humerus fractures without increasing the non-union rate.

## Background/Scientific review:

Heterotopic ossification is the formation of ectopic lamellar bone in the soft tissues. The process is thought to occur through local and distal recruitment osteoprogenitor cells especially mesenchymal stem cells which lead to HO formation based on local microenvironmental factors including activation of the BMP-mediated pathways. There are several risk factors associated with HO development such as central nervous system injury, thermal burn, hip arthroplasty, acetabular fractures, and elbow fractures; HO is also seen with certain arthropathies and genetic conditions e.g. ankylosing spondylitis, seronegative arthropathies, diffuse idiopathic skeletal hyperostosis (DISH), and fibrodysplasia ossificans progressiva. In elbow fractures the prevalence of HO is around 40%, and of those that develop HO, 20% experience a clinically relevant decrease in elbow range of motion with a flexion-extension arc of <100°. In a study by Foruria, et al. of 89 patients with a distal humerus fracture without associated proximal radius or ulna fracture that underwent surgical treatment with ORIF, 42% developed HO and the HO in these patients was associated with significantly less extension and a limited flexion-extension arc but was not associated with a change in supination or pronation. Abrams, et al. looked at the development of HO after elbow fracture fixation in 89 pts including 20 distal humerus fractures and found that distal humeral fractures were more likely to have higher grade of HO, have more compromised functional outcomes, and require return to the OR more often for capsular release with HO resection at a rate of 25%. Prophylactic treatment for HO is most commonly achieved through the use of NSAIDs such as indomethacin and radiation therapy. Both modalities have the risk of nonunion of fracture and radiation therapy has additional risks such as delayed wound healing, soft tissue contracture, and the theoretical risk of malignancy although no cases of malignancy after prophylactic radiation have been reported to date. Radiation therapy in the prevention of HO has been well studied in the hip with low-dose radiation being established as an effective dose and 700cGy as the most commonly used dose. Radiation therapy in the prevention of HO at the elbow is not as well studied and existing studies have commonly used a dose of 700cGy. One study looked at the use of radiation therapy in combination of patients being treated acutely for elbow trauma and patients being treated for HO after previous elbow trauma, and the study found that 3 of the 36 patients developed new HO and found an occurrence of 2 nonunion with the majority treated with 700cGy but 2 pts received 600cGy. Heyd, et al. present a case series of 9 patients that underwent surgical excision of clinically significant HO at the elbow and received radiation therapy of 2 doses of 500cGy (5), 1 dose of 600 cGy (3), or 1 dose of 700 cGy (1); at a mean follow up of 7.7 no patients had recurrence of HO and 8 of 9 showed clinical improvement. A study of 11 patients that underwent ORIF for fracture-dislocation of the elbow and single dose radiation therapy of 700 cGy within 72 hours postoperatively, and 3 patients (27%) developed radiographic evidence of HO while 10 patients (91%) had no functional

limitations and 100% of patients completely healed there fracture without complications at average follow up of 12 months (9-24 months). 3 of the 11 patients had distal humerus fractures and none of them had radiographic evidence of HO or functional limitation. A recent multicenter randomized control trial of patients with intraarticular distal humerus fractures or fracture-dislocation of the elbow with proximal ulna and/or radius fracture randomized patients to either receive a single dose of 700cGy within 72 hours postop or receive nothing for HO prophylaxis. Although, HO occurrence in the 21 patients in the treatment group vs the 24 in the control group (33% vs 54%), the rate of nonunion was higher in the treatment group (38% vs 4%) resulting in termination of the study. Several studies has demonstrated the efficacy and safety of radiation therapy in the prophylactic treatment of HO in elbow, but the study by Hamid questions the use of a 700 cGy dose because of the rate of nonunion observed. Thus we hypothesize that a dose of 500 cGy will be adequate in the elbow HO prevention as there is smaller treatment area compared to the hip where 700 cGy is an effective dose, and that this dose will not result in an increased rate of nonunion.

### **Study Design:**

Prospective, randomized, un-blinded study taking place at the University of Louisville Hospital. Patients will be presented the consent form and enrolled preoperatively at the University of Louisville Hospital. Patients will be randomized into one of two groups via a standard blocked randomization table. Patients who consent will be randomized into either treatment group or the control group, i.e. no medical or radiation therapy heterotopic ossification prophylaxis.

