#### **DSMC Review**

An independent committee, called the Data Safety and Monitoring Committee (DSMC) will review the progress of the study and monitor subjects' accrual, serious adverse events and unexpected events. Through this process the DSMC is also assessing the continuing validity and scientific merit of the trial. The DSMC members are from the Study Chair's Institution, the Brown Cancer Center, University of Louisville. Members on the committee view themselves as representing the interests of the study patients and not that of the institution. The DSMC makes written reports summarizing their findings at each review.

The DSMC meets quarterly, or more frequently if requested by the Principal Investigator.

The study statistician will provide the DSMC interim analysis reports determined by statistical methods noted in this protocol.

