**Outcome Measurements:**

Presence of heterotopic ossification on plain radiographs taken in the anteroposterior and lateral planes at six weeks, three months, and six months quantified using the classification systems described by Brooker, et al. and Hastings and Graham.

Clinical function measured using the Mayo Elbow Performance Score and elbow range of motion in flexion and extension, and in supination and pronation assessed at six weeks, three months, and six months. Additionally, patient health status using the 36-Item Short Form Survey (SF-36) will be assessed at six weeks, three months, six months, and one year. Fracture healing also assessed on aforementioned plain films and intervals, the interval check for nonunion will be performed every 6 months.

Complications – need for revision surgery, surgery for excision of HO or capsule release, and nonunion.

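### The protocol labels the whole study un-blinded and provides no masked reading of the films behind HO and fracture healing, so it permits open grading that could easily be masked

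*Protocol*

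**What the plan says.** The Study Design section of the protocol calls the trial a "Prospective, randomized, un-blinded study". The label covers the whole study. The control arm receives no HO prophylaxis, and no sham procedure is described.

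The Outcome Measurements section defines the HO outcome as "Presence of heterotopic ossification on plain radiographs taken in the anteroposterior and lateral planes at six weeks, three months, and six months", graded on two named classification systems. For union it says: "Fracture healing also assessed on aforementioned plain films and intervals". It names no reader and does not say whether the reader knows the arm. Nonunion also appears there in the list of complications.

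The section on confidentiality restricts collection and review of the data to the research team. The DSMC Review section gives the committee a monitoring role and does not describe it as reading films. Apart from the one word in Study Design, nothing in the protocol mentions blinding, masking, or independent or central reading.

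The Hypothesis section states that radiation "will decrease the incidence and severity of heterotopic ossification in distal humerus fractures without increasing the non-union rate".

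**The concern.** HO presence, HO grade and fracture healing are visual judgements on plain films, and the two halves of the hypothesis draw on them. A reader who knows the arm can lean one way on a borderline film. For HO the likely lean is towards the hypothesis: fewer calls on radiation, more in the untreated arm. For non-union the direction is open. The hypothesis would favour under-calling on radiation. The earlier 700 cGy trial described in the Background, where "the rate of nonunion was higher in the treatment group (38% vs 4%) resulting in termination of the study", could lead a reader to over-call it.

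Patients and treating staff cannot practically be masked against an untreated control. The films can. The views and visits are the same in both arms, the films are collected in any case, and nothing in the protocol suggests that a film itself shows whether radiation was given. At stake are the error rate of the HO comparison, its estimated size, and the credibility of a finding on non-union in either direction.

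**Working it through.** **The passages side by side.** Study Design sets un-blinded for the study as a whole. Outcome Measurements takes HO and healing from films without naming a reader. No section narrows the first statement for the purposes of the second. Open grading is therefore consistent with the protocol as written, though not ordered by it.

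**What can be put in numbers.** The protocol gives no misreading rate and no reader agreement, so the effect can only be illustrated. The protocol states no figure of its own on this point to reproduce.

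Inputs from the protocol:
- n = 45 per arm and alpha 0.05 (Sample Size).
- True HO rate p = 0.42, from the distal humerus series in the Background. It is not stated as a design input.

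Inputs that are assumed:
- Two-sided testing; the protocol gives neither sidedness nor a test, so a pooled z test and Fisher's exact test are both shown.
- The misreading fraction f: in the radiation arm a fraction f of true HO is missed, and in the control arm a fraction f of clear films is called HO.
- No true treatment effect.

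Observed rates: control = p + (1 − p)f; radiation = p(1 − f).
- f = 0.05 in both arms: 0.42 + 0.58 × 0.05 = 0.449 against 0.42 × 0.95 = 0.399, a spurious difference of 5.0 points.
- f = 0.10 in both arms: 0.42 + 0.058 = 0.478 against 0.42 × 0.90 = 0.378, 10.0 points.
- f = 0.10 in the radiation arm only: 0.420 against 0.378, 4.2 points.
- f = 0.10 in the control arm only: 0.478 against 0.420, 5.8 points.
- f = 0.10 each way in both arms alike: 0.42 × 0.90 + 0.58 × 0.10 = 0.436 in both, no difference.

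The false-positive rate is the sum of the product of the two binomial probabilities over all 46 × 46 possible outcomes in which the test rejects:

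| Assumed misreading | Spurious difference (points) | Pooled z | Fisher |
|---|---|---|---|
| None | 0 | 4.7% | 2.9% |
| 10%, unrelated to arm | 0 | 4.6% | 2.8% |
| 5%, both arms, opposite directions | 5.0 | 7.2% | 4.7% |
| 10%, radiation arm only | 4.2 | 6.7% | 4.4% |
| 10%, control arm only | 5.8 | 7.9% | 5.2% |
| 10%, both arms, opposite directions | 10.0 | 15.2% | 10.9% |

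**Sensitivity to the true rate.** For the 10% two-arm case, p = 0.40 gives 15.6% (z) or 11.2% (Fisher), and p = 0.54 gives 14.8% or 10.4%. The result depends little on p within the range of HO rates without prophylaxis in the Background.

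**Scale.** The HO difference in the earlier 700 cGy trial was 54% − 33% = 21 points. A spurious 5 points is 5/21 = 24% of that, and 10 points is 10/21 = 48%.

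No comparable calculation is offered for non-union, because the direction of any bias is not known.

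**The case against.** The strongest reply is that the defect is a silence. Un-blinded is a one-word label beside an untreated control, where it naturally describes patients and treating staff. The protocol does not say that film readers know the arm, and reading instructions could sit in a document not available here. This lowers certainty. It does not dispose of the point: whether graders know the arm is a matter of design, the protocol does address blinding, and it makes no exception. A later analysis plan cannot mask films already graded openly.

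Second, the bias is assumed throughout. Fixed views, fixed visits and two named classification systems give the reads some structure. Under Fisher, only the case of 10% in opposite directions in both arms clearly exceeds 5%, and it requires readers both to miss HO on radiation and to invent it on control films. Since no test is fixed, the larger z figures cannot be preferred. This stands in full and limits what can be claimed.

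Third, non-union is also listed as a complication, and the protocol does not say that it is determined from films alone. This also stands. The films are central to the non-union half of the hypothesis but may not be its only source.

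A reader might infer that the protocol has readers grading with the arm in view, or that the trial's HO result will be materially biased. The document supports neither. It leaves open grading possible and gives nothing from which a bias could be estimated.

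**Conclusion.** The point holds as a design weakness. The protocol labels the entire study un-blinded and masks no film reading, so outcomes central to the hypothesis may be graded with knowledge of the arm when this could cheaply be avoided.

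Harm is plausible but not shown. In the illustration, misreading of 5% in both arms leaves Fisher just under 5% and takes the z test a little above it. Clear inflation under both tests, to 15.2% or 10.9%, needs 10% in opposite directions in both arms. Misreading unrelated to arm does not inflate the rate. These figures rest on an assumed true HO rate of 42% in both arms, two-sided testing, and misreading fractions that do not come from the protocol.

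No error rate or direction is claimed for non-union. The change is one the sponsor should make, and confidence is medium.

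**What to change.** Restate the design as open-label for patients and treating staff, with masked research grading of radiographs. The films already collected are stripped of identifiers and coded. The study's existing film reader then grades them for HO and radiographic union, without access to allocation at the time of grading.

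State that these masked grades are the analysed HO and radiographic union outcomes, and that the masked union grade is the one used for the hypothesis's non-union comparison. Non-union diagnosed in care is reported separately as a complication, so that two records do not compete for the same question. Reads for patient care and safety reporting stay open and do not wait for the masked grades.

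The cost is protocol wording, coordinator time for coding, and a short delay in research grades. No extra films or patients are needed. Protection is partial: a reader may recognise a film, random misreading remains, and range of motion, the Mayo score, SF-36 and reoperation stay unmasked.

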### **Exclusion Criteria:**

1. Patient has a concomitant proximal ulna and/or proximal radius fracture
2. Patient requires external fixation of the elbow
3. Patient has a concomitant central nervous system injury or GCS <13 at time of surgery
4. Patient has quadriplegia or paraplegia
5. Patient requires intubation upon admission or for >4 hours during admission for nonsurgical purposes
6. Patient has concomitant soft tissue damage in the affected elbow that cannot be appropriately closed within 72 hours of surgery
7. Patient has a burn affecting greater than or equal to 20% of the total body surface area or on the affected elbow
8. Patient has pre-existing heterotopic ossification in the affected elbow

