### **Sample Size:**

Power analysis has been performed demonstrating 45 patients per treatment group would provide an alpha of 0.05 and a beta of 0.80.

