### **Subject Registration and Data Collection**

8.1.1 Subject registration: The informed consent process must be completed prior to initiation of any study required activities. Registration into the study will occur when the following criteria are met:

- Patient meets all inclusion and no exclusion eligibility criteria
- Patient provides written informed consent

8.1.2 Patient study identification numbers will be assigned in ascending order. This patient identifier will be recorded in the Subject Enrollment Log and placed on the header of all case report forms and study related materials to identify the subject. Subject data will be recorded in a secure location and database in the Clinical Trials Office.

8.2.1 Data Collection: Data will be collected according to the protocol requirements for all patients registered to the trial, including early termination and patients deemed ineligible.

8.3.1 The study chair and project team will collect monthly reports of the study project and accrual.

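### A blocked randomization table in an un-blinded, single-hospital trial with no allocation concealment described: assignments can be foreseen if the blocks are fixed and known, or if recruiters can see the table

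*Protocol*

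**What the plan says.** The Study Design section of the protocol gives the whole allocation procedure.

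- Setting: "Prospective, randomized, un-blinded study taking place at the University of Louisville Hospital".
- Enrolment: "Patients will be presented the consent form and enrolled preoperatively at the University of Louisville Hospital".
- Method: "Patients will be randomized into one of two groups via a standard blocked randomization table".
- Order and arms: "Patients who consent will be randomized into either treatment group or the control group, i.e. no medical or radiation therapy heterotopic ossification prophylaxis".

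The Subject Registration and Data Collection section makes registration depend on eligibility and written consent. It gives the Clinical Trials Office a data-storage role ("Subject data will be recorded in a secure location and database in the Clinical Trials Office") but no part in assignment. The locked office in the Data Management section holds data sheets and consents; the table is not mentioned. No section states the block size, whether it varies, who generates or holds the table, or how an assignment is released.

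**The concern.** Blocking forces the arms to balance at short intervals. Anyone who sees all past assignments and knows where a block ends can deduce some of the next ones. Here past assignments are visible, because controls receive no prophylaxis and the study is open at a single hospital. Concealment of the next assignment is then the main protection against selective entry, and the protocol describes none.

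There is a motive in the protocol itself. The Background reports a randomized trial of 700 cGy with less HO in the treated group (33% vs 54%) but more nonunion (38% vs 4%), which was terminated. A recruiter who expects radiation next may hesitate over a fracture that looks unlikely to heal. One who expects control next may hesitate over an elbow prone to HO.

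There is also room for discretion, in whom to approach and in exclusions that need judgement, such as "Patient has concomitant soft tissue damage in the affected elbow that cannot be appropriately closed within 72 hours of surgery". HO and nonunion are the outcomes named in the Hypothesis. An analysis plan cannot undo selection at entry.

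**Working it through.** **Inputs.** The plan gives no figure for predictability, so there is none to reproduce. From the Sample Size section: 45 per group, hence 2 × 45 = 90 patients and, by inference, 1:1 allocation. Assumed because the protocol is silent: fixed block size B = 2, 4, 6, 8 or 10, known to staff, with all past assignments visible.

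**1. Assignments that are certain.** In a 1:1 block of size B = 2h, the rest of the block is certain once one arm is used up. Averaged over all orderings, the certain share is 1/(h + 1). For B = 4 the orderings are AABB, ABAB, ABBA and their mirror images, with 2, 1 and 1 certain assignments. The mean is 4/3 per block, and (4/3)/4 = 1/3.

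**2. Best guess.** Always naming the arm that is behind, and tossing a coin when level, is right for a share [h + (4^h / C(2h, h) − 1)/2] / (2h). For B = 4: [2 + (16/6 − 1)/2]/4 = 2.833/4 = 0.708.

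| Block size | Certain | Of 90 | Best guess right |
|---|---|---|---|
| 2 | 50% | 45 | 75.0% |
| 4 | 33.3% | 30 | 70.8% |
| 6 | 25% | 22.5 | 68.3% |
| 8 | 20% | 18 | 66.6% |
| 10 | 16.7% | 15 | 65.3% |

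These are averages over whole blocks; 90 is not a multiple of 4 or 8, so those counts are approximate. If recruiters can see the table, 100% are known.

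**3. Varied, undisclosed block sizes.** In simulated lists of 90, an observer using only the running imbalance gives:

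| Sizes in the list | Certain | Best guess right |
|---|---|---|
| 4/6 | 1.0% | 69.2% |
| 2/4/6 | 0.8% | 70.2% |
| 4/6/8 | 0.2% | 67.9% |

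The certain shares here are not counted as in step 1. There, staff know the block size and use the whole history; counted from the running imbalance alone, fixed blocks of 4 give 8.2%. For a like-for-like comparison I repeated the simulation with an observer who knows the set of sizes and tracks the full history. The certain share is then about 5.5%, 4.0% and 2.3% for the three mixes, against 33% for fixed blocks of 4. The best-guess rates do not change.

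**4. What this means for the remedy.** Varied blocks remove most of the certainty, more so if the sizes stay undisclosed. They hardly lower the best-guess rate (about 68% to 70%, against 70.8% for fixed blocks of 4), because the running imbalance stays visible.

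**The case against.** The strongest reply is that this is largely silence. The section commits to blocking but not to fixed blocks, a known block size or a table in recruiters' hands, and a varied-block table would fit the same words. Blocking in an open single-site trial is not an error. Leaving the block size out of a document that recruiters read is normal and protects concealment. Generation and custody may be set out in a document not shown. All of this stands, and it makes the point conditional. It does not remove it: the protocol fixes the method and the open setting, and how assignments are concealed and released is trial conduct.

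Three stronger readings are tempting and are not supported.

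- A reader might infer that enrolling staff can in fact work out upcoming assignments. That needs fixed blocks whose size they know or infer, or sight of the table, and the protocol states neither. Even with known blocks of 4, two-thirds of assignments are not certain.
- A reader might put a size on the bias. If patients had HO risks of 30% or 60% and every enrolment were steered on the best guess, the arms would differ by (2 × 0.708 − 1) × 0.30 = 12.5 points with no treatment effect; with one in five steered, 2.5 points. The risk split and the degree of steering have no source in the protocol, so 12.5 is an assumed upper figure. Nor would the fix save it: at best-guess rates of 0.68 and 0.70 the same formula gives 10.8 and 12.0 points.
- A reader might take the 72-hour closure exclusion as evidence of guessing from blocks. Enrolment is preoperative, so that exclusion may be settled only after assignment. Exclusion with the assignment known is a related risk, but it does not depend on predicting blocks. Several other exclusions are objective.

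**Conclusion.** The concern holds in conditional form. The protocol specifies a blocked table in an un-blinded, single-hospital trial and describes no allocation concealment. If blocks are fixed and their size is known or inferred, between 17% (size 10) and 50% (size 2) of assignments are certain in advance, or about 15 to 45 of 90. If recruiters can see the table, all are. These figures rest on assumed block sizes and 1:1 allocation. The documents do not show that any assignment has been or will be foreseen, and they support no figure for the resulting bias in HO or nonunion. The change is worth making because it is cheap and selection at entry cannot be repaired later.

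**What to change.** In Study Design, replace the table with permuted blocks of randomly varying size, with the sizes not disclosed to enrolling staff. Have the study statistician generate the list and someone not involved in recruitment hold it. The existing Clinical Trials Office could do this if it can cover the times when patients are enrolled, which the protocol does not show. Otherwise use sequential, sealed, opaque envelopes. Release each assignment only after consent, eligibility and registration are recorded. If such a procedure already exists elsewhere, the protocol should say so.

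The cost is a short protocol change, a new list for the remaining patients, one extra step at each assignment, and possibly an imbalance of a few patients at the end.

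Two limits remain. Staff can still guess from visible past assignments better than by chance. And where an exclusion can be settled only after release, this change does not prevent its being applied with the assignment known.
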